8.2.2. Summaries of Adverse Events of Special Interest

Adverse events of special interest (AESI) in the CY 5032 study are defined based on clinical and laboratory parameters. Results for AESI will be reviewed individually. No summary table will be provided.

Clinically significant elevated transaminases and/or (total and if available, direct) bilirubin and manifestations of liver toxicity (e.g., rash, abdominal pain, nausea and vomiting, fatigue, dark-colored urine, light-colored bowel movements, jaundice, loss of appetite, fever) including elevations that prompt study drug discontinuation are considered adverse events of special interest and should be reported to Cytokinetics Drug Safety within 24 hours of awareness on an AESI Report Form.

Any of the following criteria should be reported as Liver-Related AESIs:

- Manifestations of liver toxicity
- ALT or AST $>8 \times$ ULN
- ALT or AST $>5 \times$ ULN but $<8 \times$ ULN for ≥ 2 weeks
- ALT or AST $> 5 \times$ ULN but $<8 \times$ ULN and unable to adhere to monitoring
- ALT or AST $>3 \times$ ULN w/signs or symptoms consistent with hepatitis (i.e., right upper quadrant pain /tenderness, fever, nausea, vomiting, jaundice)
- TBL $>3 \times$ ULN
- TBL $>2 \times$ ULN or INR >1.5 AND ALT or AST $>3 \times$ ULN AND no alternative cause is apparent

Manifestations of renal toxicity, including clinically significant decreases in $eGFR_{Cr}$ and $eGFR_{CysC}$ and increases of UPCr, are also considered adverse events of special interest and should be recorded on the appropriate CRF and reported to Cytokinetics Drug Safety within 24 hours of awareness on an AESI Report Form.

Any of the following criteria should be reported as Renal-Related AESIs:

- Manifestations of renal toxicity
- Both $eGFR_{Cr}$, $eGFR_{CysC} < 30.0$ ml/min/1.73m²

- UPCR \geq 3 mg protein/g creatinine (or \geq 339 mg protein/mmol creatinine)

In addition, if reldsemtiv has been temporarily interrupted or permanently discontinued related to renal labs that don't meet the above criteria, this is also considered as Renal-Related AESIs. Study drug dose management with the potential for a dosing interruption and down-titration of dose will be applied.

8.3. Total Duration of Therapy, Average Daily Dose, Maximum Daily Dose, Final Daily Dose of Study Medication, and Compliance

Total duration of treatment and exposure of study drug per day will be summarized overall.

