2.3.1.1. Mitigation Strategy

For both the renal and hepatic findings in CY 5022, the frequency was highest in those patients on the highest dose of reldesemtiv (450 mg twice a day); thus, the highest dose that will be used in this OLE is reldesemtiv 300 mg twice a day and careful monitoring of renal function and liver enzymes will be implemented during the trial.

Renal Safety

For renal safety, the mitigation strategy includes renal function monitoring and detailed study drug dose management with the potential for a dosing interruption and down-titration of dose, as described in [Section 7.3](#).

Hepatic Safety

For hepatic safety, the mitigation strategy includes liver function monitoring and reldesemtiv discontinuation criteria as described in [Section 7.4](#).

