8.3. Adverse Events and Serious Adverse Events

8.3.1. Adverse Events

8.3.1.1. Definition of Adverse Event

An AE is defined as any untoward medical occurrence in a patient or clinical investigation patient administered a pharmaceutical product and which does not necessarily have a causal relationship with this treatment. An AE can therefore be any unfavorable and unintended sign (including an abnormal laboratory finding), symptom, or disease temporally associated with the use of study drug, whether or not related to study drug.

Adverse events include:

- Exacerbation of a chronic or intermittent pre-existing condition (a condition that occurred before the patient was exposed to reldesemtiv) including either an increase in frequency and/or intensity of the condition.
- New conditions detected or diagnosed after IP administration even though it may have been present before the start of the trial.
- Abnormal assessments, eg, change on physical examination, electrocardiogram (ECG) findings, if they represent a clinically significant finding that was not present at trial start or worsened during the course of the trial.
- Laboratory test abnormalities if they represent a clinically significant finding, symptomatic or not, which was not present at trial start or worsened during the course of the trial, require treatment, or led to dose reduction, interruption or permanent discontinuation of IP. In general, abnormal laboratory findings without clinical significance (based on the investigator's judgment) are not to be recorded as adverse events. Where applicable, clinical sequelae (not the laboratory abnormality) are to be recorded as the adverse event.
- Signs, symptoms, or the clinical sequelae of a suspected drug-drug interaction.
- Signs, symptoms, or the clinical sequelae of a suspected overdose of either study drug or a concomitant medication. Overdose per se will not be reported as an AE/SAE unless it is an intentional overdose taken with possible suicidal/self-harming intent. Such overdoses should be reported regardless of sequelae.

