9.2.4.1. Adverse Events

A treatment-emergent adverse event (TEAE) is an AE with an onset after initiation of study drug dosing in CY 5032, or an AE present at initiation of study drug dosing that worsens in severity after initiation of study drug dosing. All AE terms will be coded using the Medical Dictionary for Regulatory Activities (MedDRA). Primary system organ class (SOC) and preferred term (PT) of the TEAEs will be tabulated by the early-start and delayed-start treatment groups. TEAEs will also be summarized by severity and relationship to study drug. AEs that led to early discontinuation from treatment or the trial and adverse events of special interest will be summarized. Listings will be presented for patients who discontinued due to TEAEs.

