1. INTRODUCTION

This document describes the plan for the summarization and analysis of clinical data collected in CY 5032, an open-label extension of CY 5031. CY 5031 was terminated early by the Sponsor due to meeting the futility criteria at the CY 5031 second planned interim analysis. As a result, the analysis scope has been abbreviated, and certain analyses outlined in the protocol will not be conducted, see Section 9 for details.

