4.2. Final Analyses

The final analysis was planned to be performed when all patients who enrolled in the CY 5032 study have completed the study, all outstanding queries resolved, and the database cleaned and finalized.

Since the study was terminated early by the Sponsor due to futility in the parent study, after the database has been cleaned to the extent for safety assessments and locked, one final analyses of all data will be conducted for an abbreviated CSR.

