8.2. Adverse Events

8.2.1. Summaries of Adverse Event Incidence Rates for All Subjects

Adverse events (AEs) will be coded by System Organ Class (SOC) and Preferred Term (PT) using the Medical Dictionary for Regulatory Activities (MedDRA) version 26.0.

Analyses of AEs will be performed for those events that are considered treatment emergent AEs (TEAEs), where treatment emergence is defined as any adverse events with an onset after initiation of study drug dosing in CY 5032, or an AE present at initiation of study drug dosing that worsens in severity after initiation of study drug dosing. If an AE had the onset in the preceding study CY 5031 and carry over to the open-label extension, it will not be considered as treatment emergent in CY 5032 data.

The following summaries of AEs and serious AEs (SAEs) will be presented by overall:

- TEAEs by SOC and PT
- TEAEs by PT
- TEAEs by SOC, PT and Severity (Grade 1-5)
- TEAEs related to study drug by SOC and PT

- TEAEs related to study drug by PT
- TESAEs by SOC and PT
- TESAEs by PT
- TESAEs related to study drug by PT
- TEAEs leading to drug discontinuation by PT
- TEAEs leading to death

AE summaries will be presented by descending order of PT in the overall column, and if applicable, SOC will be ordered first, with PT sorted within the SOC.

A patient will be counted only once within each SOC and PT. For the summary of AEs by severity, patients will be counted only once within each primary SOC/preferred term and will only be counted under the maximum severity.

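### SAP 8.2.2's renal UPCR criterion pairs two units that disagree by a factor of 1000, demographics use an undefined FAS, Section 9's table list conflicts with Sections 7 and 8.3, and no renal tabulation is pre-specified

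*SAP*

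**What the plan says.** The SAP is open about its reduced scope. Its Introduction says that, after the parent study stopped for futility, "certain analyses outlined in the protocol will not be conducted, see Section 9 for details", and Section 4.2 says that "one final analyses of all data will be conducted for an abbreviated CSR".

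- **Organ risks.** Protocol 2.3.1.1 names two: "For both the renal and hepatic findings in CY 5022, the frequency was highest in those patients on the highest dose of reldesemtiv". Protocol 9.2.4.1 planned that "AEs that led to early discontinuation from treatment or the trial and adverse events of special interest will be summarized".
- **AESIs.** SAP 8.2.2 repeats the protocol's liver and renal definitions and then states: "Results for AESI will be reviewed individually. No summary table will be provided". This applies to both organs.
- **Laboratory output.** SAP 8.5 keeps a table and a by-patient listing for ALT, AST, ALP and total bilirubin. Section 9 names a listing for liver abnormality only. No SAP section names a count, table or listing for eGFR, UPCR or renal-related interruptions.
- **UPCR.** Protocol 8.3.1.3 and SAP 8.2.2 set the renal AESI criterion at 3 mg/g, with 339 mg/mmol in brackets as the equivalent. Protocol 7.3 sets the hold criterion at 3 mg/mg, with the same 339 mg/mmol in brackets.
- **Analysis set.** SAP 6.3 places demographics in the FAS. SAP 5.4 defines only the Safety Analysis Set. Protocol Table 5 defines the FAS on CY 5031 data, whether or not the patient entered the extension. SAP 5.6.1 takes demographics from the CY 5032 baseline.
- **Table list.** Section 9 limits tables to disposition, demographics and baseline, an overview of AEs, and abnormal liver results. Section 7 calls for ALSFRS-R change by visit, and Section 8.3 for treatment duration and exposure.

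**The concern.** The primary objective is long-term safety, so the safety definitions and the list of outputs are the parts of an abbreviated plan that most need to be unambiguous.

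The UPCR line matters beyond tables. It is a reporting criterion with a 24-hour clock as well as a definition for case review. If its two units disagree, two people working from the same line can classify the same result differently.

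The FAS label leaves the demographic table without a defined population in the document that is meant to define it.

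The Introduction sends the reader to Section 9 to learn what has been dropped. If Section 9 is taken literally, exposure is dropped, yet exposure is needed to interpret any adverse-event frequency.

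Finally, one of the two organ risks named in the protocol keeps its laboratory table and listing, the other has neither, and the SAP gives no reason for the difference.

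**Working it through.** **1. UPCR units.** The inputs are the two pairs in protocol 7.3 and the single pair in protocol 8.3.1.3, repeated in SAP 8.2.2. The mg creatinine per mmol that each pair implies is (mg/mmol figure) / (mg/mg figure).

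- Protocol 7.3, hold: 339 / 3 = 113.0
- Protocol 7.3, restart: 170 / 1.5 = 113.3
- AESI line: 3 mg/g = 0.003 mg/mg, so 339 / 0.003 = 113,000

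The two pairs in 7.3 agree within 0.3%. The AESI pair differs from them by 113,000 / 113 = 1000.

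In the forward direction, 3 mg/mg × 113 = 339 mg/mmol, which reproduces the stated figure. With the printed unit, 3 mg/g × 113 / 1000 = 0.339 mg/mmol, which does not.

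If someone used the mg/g figure alone, the restart limit in 7.3 (1.5 mg/mg = 1500 mg/g) would lie 1500 / 3 = 500 times above the AESI figure. This shows which pairs are arithmetically consistent. It does not settle what the clinical criterion should be.

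**2. Analysis set.** SAP 6.3, SAP 5.4, SAP 5.6.1 and protocol Table 5 do not fit together. The label in 6.3 has no definition in the SAP. The only definition available, in the protocol, includes patients who never entered the extension, and such patients have no CY 5032 baseline to summarise.

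**3. Section 9 against the other sections.** ALSFRS-R change by visit (Section 7) and duration and exposure (Section 8.3) are not among Section 9's four items, and Section 9 says that only those items will be tabulated. The ten AE summaries in 8.2.1 also go beyond what an overview would normally mean, but that wording could be stretched to cover them. The conflict with Sections 7 and 8.3 is plain.

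**4. Can the planned AE tables supply the renal count?** Only in part.

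- Protocol 8.3.1.1 makes clinically significant laboratory findings AEs if they "require treatment, or led to dose reduction, interruption or permanent discontinuation of IP", so renal results that lead to a hold should reach the SOC and PT tables.
- The same section adds that, where applicable, "clinical sequelae (not the laboratory abnormality) are to be recorded as the adverse event", so one criterion can appear under different terms.
- SAP 8.2.1 says "A patient will be counted only once within each SOC and PT". One patient can therefore appear in several PT rows, and adding rows does not give a number of patients. An SOC row does count patients, but it is not restricted to those who met a renal criterion.
- The overview in SAP 8.1 has no breakdown by organ.

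No output named in the SAP text therefore gives the number of patients who met a renal criterion.

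**The case against.** The strongest reply is that the renal item is a matter of scope. The early termination is disclosed, and individual AESI review replaces the planned summary for both organs alike. The protocol also offers some basis for the liver emphasis: the Week 6 and Week 18 remote samples are liver tests only, and the liver thresholds in 7.4 lead to permanent discontinuation, whereas the renal thresholds in 7.3 lead to a hold with possible restart. All of this stands. The SAP does not give it as its reason, but it is why the renal count is presented here as a cheap improvement and not as an error.

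A reader might infer that the report could not state a renal incidence at all. The documents do not support that. Renal AESIs are to be recorded and reported within 24 hours, each is reviewed, and disposition gives the number of patients who received a dose, so cases over N can be stated. A renal listing may also exist in the display specifications, which SAP 11.1 and 11.2 place in a separate document that was not available. SAP 5.3 promises listings that support the tables, but no renal table is named for one to support.

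A reader might also infer that UPCR results will be misclassified. That would require using the mg/g figure and ignoring the 339 mg/mmol beside it, which matches protocol 7.3. The wording is also inherited from protocol 8.3.1.3 and did not originate in the SAP.

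Lastly, a reader might infer that demographics will describe a materially different set of patients from the AE tables. SAP 5.6.1 limits that, because patients outside the extension have no CY 5032 baseline. Those who entered had completed CY 5031 dosing, so nearly all should meet the protocol's FAS definition.

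**Conclusion.** Three points are wrong as written and need correcting.

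- **UPCR.** The two units in the AESI line disagree by a factor of 1000, by the documents' own conversion. This is arithmetic and rests on no outside figure. Whether any patient is affected depends on which unit is used, and the documents do not say.
- **FAS.** The label is undefined in the SAP and does not fit the CY 5032 baseline. The numerical effect is probably small, but it cannot be calculated because the size of the CY 5031 FAS is not given.
- **Section 9.** Its list contradicts Sections 7 and 8.3, and it is left open whether exposure will be tabulated.

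The fourth point is an improvement: liver output is pre-specified, no renal tabulation is, and the AESI summary planned in the protocol has been dropped. That conclusion is limited to the SAP text, since the display specifications were not available.

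**What to change.** 1. Before the UPCR criterion is used for AESI reporting, review or programming, the sponsor reconciles its units across protocol 7.3, protocol 8.3.1.3 and SAP 8.2.2.
2. In SAP 6.3, replace FAS with Safety Analysis Set.
3. Reconcile Section 9's list with Sections 7 and 8.3 so that it is clear that exposure will be produced, and state in the same edit whether the 8.2.1 tables are.
4. In SAP 8.2.2, replace the sentence that rules out a summary table with two rows for the Safety Analysis Set: the number and percentage of patients with at least one liver-related AESI, and the number and percentage with at least one renal-related AESI, each with onset on or after the first CY 5032 dose. Individual review can continue alongside.
5. Add a by-patient listing of eGFR_Cr, eGFR_CysC and UPCR for patients who meet a renal criterion, using the reconciled units.

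The cost is one small table, one listing, a few wording edits and one units reconciliation. No new data are needed: full chemistry and UPCR are already scheduled at Day 1 and Weeks 12, 24, 36, 48 and 52. Completion after the early termination is not reported, so later visits may contribute few results to the listing.

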8.4. Concomitant and Other Medications

Concomitant medications reported on the eCRF will be listed. The WHO Drug Dictionary will be used to classify medications by therapeutic class (ATC Class 3) and preferred name. Coding will be performed using WHO Drug Dictionary Enhanced with Herbal Dictionary, B3, SEP 2020.

8.5. Clinical Laboratory Data

Abnormal post-baseline results in Alanine Aminotransferase (ALT), Aspartate Aminotransferase (AST), Alkaline Phosphatase (ALP) and Total Bilirubin (BILI) will be summarized by overall in the Safety Analysis Set, with the following categories:

For ALT or AST:

- \leq Upper Limit of Normal (ULN),
- $>$ ULN - 3x ULN,
- $>$ 3x ULN - 5x ULN,
- $>$ 5x ULN - 8x ULN,
- $>$ 8x ULN

For Total Bilirubin:

- \leq ULN,
- $>$ ULN - 2x ULN,
- $>$ 2x ULN – 3x ULN
- $>$ 3x ULN

For more than one liver function test:

- ALT or AST $>$ 3x ULN and total bilirubin $>$ 2x ULN
- ALT or AST $>$ 3x ULN and total bilirubin $>$ 2x ULN and ALP $<$ 2xULN
- ALT or AST $>$ 3 x ULN with signs/symptoms including nausea, vomiting, abdominal pain, fatigue, rash, dark-colored urine, light-colored bowel movements, jaundice, loss of appetite or fever.

The lower limit of normal (LLN) and upper limit of normal (ULN) provided by the laboratories will be used as the criteria to determine abnormality. For each parameter, the denominator of the percentage will include patients with normal or missing assessments at baseline, and with at least

one assessment post-baseline. The numerator of the percentage will include patients who had at least one abnormal assessment post-baseline among the patients that were counted in the denominator. Assessment collected at unscheduled visits or the Follow-up Visit will be included in the summary.

Patients fulfilling any of the individual criteria (ALT/AST, ALP, or BILI) will be listed, and the listing will include all available ALT, AST, BILI, and ALP, sorted by assessment date in ascending order.

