5.4. Analysis Population

5.4.1. Safety Analysis Set

The Safety Analysis Set consists of all patients who receive any amount of study drug in this study.

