5.5. Baseline Definition

For eligible patients who consent to participate in the open-label extension, the last available assessment taken prior to the administration of the first dose of CY 5032 study drug will serve as the baseline of CY 5032.

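### The liver table in SAP 8.5 drops patients already above ULN at baseline, so their later rises are missing from that parameter's ULN-multiple rows

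*SAP*

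**What the plan says.** SAP 8.5 states that abnormal post-baseline ALT, AST, ALP and total bilirubin "will be summarized by overall in the Safety Analysis Set, with the following categories". SAP 5.4.1 defines that set without regard to baseline laboratory status: "The Safety Analysis Set consists of all patients who receive any amount of study drug in this study". The ALT or AST bands run from at or below ULN up to above 8x ULN, and the bilirubin bands from at or below ULN up to above 3x ULN. A further block is headed "For more than one liver function test".

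The same section then sets the rule for the percentages. Laboratory limits "provided by the laboratories will be used as the criteria to determine abnormality". Who is counted is then decided separately for every liver test: "the denominator of the percentage will include patients with normal or missing assessments at baseline", with at least one post-baseline assessment also required. The numerator is patients with at least one abnormal post-baseline value "among the patients that were counted in the denominator". Values from unscheduled and follow-up visits count.

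SAP 5.5 fixes the CY 5032 reference value: "the last available assessment taken prior to the administration of the first dose of CY 5032 study drug will serve as the baseline". The definition in SAP 8 is to the same effect. SAP 8.5 also provides a listing: "Patients fulfilling any of the individual criteria (ALT/AST, ALP, or BILI) will be listed".

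**The concern.** The stated population is everyone treated, but the percentage rule covers only those with a normal or missing baseline for the parameter. Restricting to a normal baseline is a legitimate way to report *newly abnormal* incidence. SAP 8.5 does not label it that way, however, and the inclusion of missing baselines means it is not cleanly that either.

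The choice matters more here than in a trial with a drug-free baseline. Protocol 2.3.1 says every patient will have had at least 24 weeks of reldesemtiv before entering. A patient whose enzymes rose during CY 5031 and stayed up is the kind of patient the rule removes.

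Protocol 2.3.1.1 names liver enzymes as a monitoring concern, and SAP 9 keeps abnormal liver results as the only laboratory table. What is at stake is an incomplete count of patients crossing each ULN multiple in that table.

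**Working it through.** The plan gives no figure to reproduce, so the check traces the rule and then shows what it does to counts and percentages under stated assumptions.

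**1. Trace one patient.** Take a baseline ALT of 2x ULN that rises to 9x ULN. Judged against the laboratory ULN, the baseline is abnormal, so the patient is outside the ALT denominator. The numerator is confined to that denominator, so the patient is not counted for ALT above 8x ULN. A patient with a normal or missing baseline ALT and the same peak is counted. The same logic applies to AST and bilirubin.

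**2. Can such patients enter?** Protocol 5.1 and 5.2 set no general enzyme limit. The Day 1 laboratory check (Protocol 1.3 and 8) applies only when Day 1 falls more than 6 weeks after the CY 5031 follow-up visit. It requires ALT/AST below 3x ULN, so values between 1x and 3x ULN still pass. Completing CY 5031 dosing is some filter on tolerance but does not rule out an elevated value.

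**3. Does the rule fit the table?** The numerator needs an abnormal post-baseline value. A patient who stays within normal limits is never in it, so the row for values at or below ULN cannot be filled as intended. For the combined rows the denominator is not stated.

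**4. Effect on counts and percentages.** Let q be the share above ULN at baseline, RR their relative risk of crossing a threshold, and p0 the risk with a normal baseline. Neither q nor RR is in the documents; both are assumed.

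- True percentage = p0 × [(1 − q) + q × RR]
- Reported percentage = p0
- Share of cases omitted = q × RR / [(1 − q) + q × RR]
- Reported / true = 1 / [(1 − q) + q × RR], so p0 cancels

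For q = 10% and RR = 2, the bracket is 0.90 + 0.20 = 1.10. The omitted share is 0.20/1.10 = 18.2% and the ratio is 1/1.10 = 0.91.

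| q | RR | Cases omitted | Reported / true |
|---|---|---|---|
| 5% | 0.5 | 2.6% | 1.03 |
| 5% | 1 | 5.0% | 1.00 |
| 5% | 2 | 9.5% | 0.95 |
| 10% | 0.5 | 5.3% | 1.05 |
| 10% | 1 | 10.0% | 1.00 |
| 10% | 2 | 18.2% | 0.91 |
| 20% | 0.5 | 11.1% | 1.11 |
| 20% | 1 | 20.0% | 1.00 |
| 20% | 2 | 33.3% | 0.83 |

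**5. In patients.** SAP 3.2 anticipates about 400. The study stopped early and actual enrolment is not given, so 400 is illustrative. At q = 5%, 10% or 20%, the rule leaves 20, 40 or 80 patients out of a parameter's rows. At q = 10%, suppose the only case above 8x ULN is among the 40 left out. The row reads 0/360 (exact 95% CI 0 to 1.0%) instead of 1/400, or 0.25% (exact 95% CI 0.01% to 1.4%).

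**6. Do other outputs supply the count?**

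- The listing in SAP 8.5 states no baseline restriction and shows all liver values for those listed, but it is not a tabulated incidence.
- SAP 8.2.2 reviews adverse events of special interest individually, without a summary table.
- Under Protocol 8.3.1.1, clinically significant rises, or rises leading to dose reduction, interruption or discontinuation, are adverse events, so many will reach the tables in SAP 8.1 and 8.2.1. Those tables are by preferred term and severity grade, not ULN multiple.
- SAP 8.2.1 also says an event with onset in CY 5031 that carries over is not treatment-emergent, although its preceding sentence counts worsening. A worsening elevation already recorded in CY 5031 may be missed there too.

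**The case against.** The strongest counter-argument uses the table's own awkwardness. Because the row for values at or below ULN cannot be filled from abnormal patients, the denominator sentence may be generic wording for a newly-abnormal percentage, with the ULN bands meant as an ordinary classification of all treated patients. The display specifications, which might settle this, are in a separate document (SAP 11.1 and 11.2) and cannot be checked here. But SAP 8.5 describes no other percentage for the sentence to govern, and naming normal or missing baselines would serve no purpose if all patients were counted. Restriction is the natural reading.

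Two points limit the scope. ALT and AST share one block, so a patient elevated at baseline only for ALT may still be counted through AST. Patients left out of a parameter's own rows may also count in the combined rows.

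It is also fair that extreme cases are well covered elsewhere. Protocol 7.4 makes ALT or AST above 8x ULN a criterion for permanent discontinuation at any baseline. Such a patient would be listed, reviewed as an event of special interest, normally recorded as an adverse event, and reflected in the discontinuation reasons under SAP 6.1. This limits the harm but does not restore the count in the table.

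Finally, the size and even the direction of any bias are unknown, and this is a descriptive table for an abbreviated report. That argues for a modest grading, not for leaving the rule as it is.

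**Conclusion.** The concern holds. As written, SAP 8.5 excludes patients above ULN at CY 5032 baseline from that parameter's ULN-multiple rows, while naming a population that includes them. The result is an incomplete laboratory incidence, not concealment.

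The size cannot be determined from the documents. Over the assumed range of q from 5% to 20% and RR from 0.5 to 2, between 2.6% and 33.3% of cases are omitted, and the reported percentage is between 0.83 and 1.11 of the true one. With equal risk only the counts are short. This should be fixed before the table is produced. Confidence is medium, because the display specifications are not available and the frequency of elevated baselines is unknown.

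**What to change.** In SAP 8.5:

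- Classify every Safety Analysis Set patient with at least one post-baseline value by maximum post-baseline category, including unscheduled and follow-up values. Use that denominator for all ULN-multiple rows, including the row at or below ULN.
- State the denominator for the combined rows.
- Show results by baseline category. For ALT/AST: at or below ULN, above ULN to 3x, above 3x, missing. For bilirubin: at or below ULN, above ULN, missing.
- Keep the normal-baseline subset as a separate column labelled *newly abnormal*.
- Bring the separate display specifications into line.

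The cost is SAP wording and minor extra programming. No new data are needed and no clinical rule changes. Counts above each threshold can only stay the same or rise; percentages may move either way.
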